Note: The frequencies are measured as Spots per million PBMC, format is 0 - xxxx

Table 38: Frequencies of Peripheral Blood CD4+ T Cells Specific for OMV and NHBA Antigens by Time Point and Treatment Group – Intracellular Cytokine Staining (ICS), Immunogenicity Population

Assay: ICS	Phenotype	Statistic	4CMenB					Placebo				
			Day 1	Day 15	Day 29	Day 43	Day 57	Day 1	Day 15	Day 29	Day 43	Day 57
NZ98 OMV	IL17+ as a % of CD4+	N	x	x	x	x	x	x	x	x	x	x
		Mean (SD)	x(x)									
		Median (IQR)	x(x, x)									
	TNFa+ as a % of CD4+	N	x	x	x	x	x	x	x	x	x	x
		Mean (SD)	x(x)									
		Median (IQR)	x(x, x)									
	IFNG+ as a % of CD4+	N	x	x	x	x	x	x	x	x	x	x
		Mean (SD)	x(x)									
		Median (IQR)	x(x, x)									
1291 OMV	IL17+ as a % of CD4+	N	x	x	x	x	x	x	x	x	x	x
		Mean (SD)	x(x)									
		Median (IQR)	x(x, x)									
	TNFa+ as a % of CD4+	N	x	x	x	x	x	x	x	x	x	x
		Mean (SD)	x(x)									
		Median (IQR)	x(x, x)									
	IFNG+ as a % of CD4+	N	x	x	x	x	x	x	x	x	x	x
		Mean (SD)	x(x)									
		Median (IQR)	x(x, x)									
CNG20 OMV	IL17+ as a % of CD4+	N	x	x	x	x	x	x	x	x	x	x
		Mean (SD)	x(x)									
		Median (IQR)	x(x, x)									
	TNFa+ as a % of CD4+	N	x	x	x	x	x	x	x	x	x	x
		Mean (SD)	x(x)									
		Median (IQR)	x(x, x)									
	IFNG+ as a % of CD4+	N	x	x	x	x	x	x	x	x	x	x

Table 38: Frequencies of Peripheral Blood CD4+ T Cells Specific for OMV and NHBA Antigens from GC by Time Point and Treatment Group – Intracellular Cytokine Staining (ICS), Immunogenicity Population (continued)

Assay: ICS	Phenotype	Statistic	4CMenB					Placebo				
			Day 1	Day 15	Day 29	Day 43	Day 57	Day 1	Day 15	Day 29	Day 43	Day 57
			Mean (SD)	x(x)	x(x)	x(x)	x(x)	x(x)	x(x)	x(x)	x(x)	x(x)
NHBA NZ98	IL17+ as a % of CD4+	N	x	x	x	x	x	x	x	x	x	x
		Mean (SD)	x(x)	x(x)	x(x)	x(x)	x(x)	x(x)	x(x)	x(x)	x(x)	x(x)
		Median (IQR)	(x, x)	(x, x)	(x, x)	(x, x)	(x, x)	(x, x)	(x, x)	(x, x)	(x, x)	(x, x)
	TNFa+ as a % of CD4+	N	x	x	x	x	x	x	x	x	x	x
		Mean (SD)	x(x)	x(x)	x(x)	x(x)	x(x)	x(x)	x(x)	x(x)	x(x)	x(x)
		Median (IQR)	(x, x)	(x, x)	(x, x)	(x, x)	(x, x)	(x, x)	(x, x)	(x, x)	(x, x)	(x, x)
	IFNG+ as a % of CD4+	N	x	x	x	x	x	x	x	x	x	x
		Mean (SD)	x(x)	x(x)	x(x)	x(x)	x(x)	x(x)	x(x)	x(x)	x(x)	x(x)
		Median (IQR)	(x, x)	(x, x)	(x, x)	(x, x)	(x, x)	(x, x)	(x, x)	(x, x)	(x, x)	(x, x)
NHBA Ng1291	IL17+ as a % of CD4+	N	x	x	x	x	x	x	x	x	x	x
		Mean (SD)	x(x)	x(x)	x(x)	x(x)	x(x)	x(x)	x(x)	x(x)	x(x)	x(x)
		Median (IQR)	(x, x)	(x, x)	(x, x)	(x, x)	(x, x)	(x, x)	(x, x)	(x, x)	(x, x)	(x, x)
	TNFa+ as a % of CD4+	N	x	x	x	x	x	x	x	x	x	x
		Mean (SD)	x(x)	x(x)	x(x)	x(x)	x(x)	x(x)	x(x)	x(x)	x(x)	x(x)
		Median (IQR)	(x, x)	(x, x)	(x, x)	(x, x)	(x, x)	(x, x)	(x, x)	(x, x)	(x, x)	(x, x)
	IFNG+ as a % of CD4+	N	x	x	x	x	x	x	x	x	x	x
		Mean (SD)	x(x)	x(x)	x(x)	x(x)	x(x)	x(x)	x(x)	x(x)	x(x)	x(x)
		Median (IQR)	(x, x)	(x, x)	(x, x)	(x, x)	(x, x)	(x, x)	(x, x)	(x, x)	(x, x)	(x, x)
NHBA CNG20	IL17+ as a % of CD4+	N	x	x	x	x	x	x	x	x	x	x
		Mean (SD)	x(x)	x(x)	x(x)	x(x)	x(x)	x(x)	x(x)	x(x)	x(x)	x(x)
		Median (IQR)	(x, x)	(x, x)	(x, x)	(x, x)	(x, x)	(x, x)	(x, x)	(x, x)	(x, x)	(x, x)
	TNFa+ as a % of CD4+	N	x	x	x	x	x	x	x	x	x	x
		Mean (SD)	x(x)	x(x)	x(x)	x(x)	x(x)	x(x)	x(x)	x(x)	x(x)	x(x)
		Median (IQR)	(x, x)	(x, x)	(x, x)	(x, x)	(x, x)	(x, x)	(x, x)	(x, x)	(x, x)	(x, x)

Table 38: Frequencies of Peripheral Blood CD4+ T Cells Specific for OMV and NHBA Antigens from GC by Time Point and Treatment Group – Intracellular Cytokine Staining (ICS), Immunogenicity Population (continued)

Assay: ICS	Phenotype	Statistic	4CMenB					Placebo				
			Day 1	Day 15	Day 29	Day 43	Day 57	Day 1	Day 15	Day 29	Day 43	Day 57
			N	x	x	x	x	x	x	x	x	x
Consensus peptide pool	IFNG+ as a % of CD4+	Mean (SD)	x(x)	x(x)	x(x)	x(x)	x(x)	x(x)	x(x)	x(x)	x(x)	x(x)
		Median (IQR)	(x, x)	(x, x)	(x, x)	(x, x)	(x, x)					
		N	x	x	x	x	x	x	x	x	x	x
Consensus peptide pool	IL17+ as a % of CD4+	Mean (SD)	x(x)	x(x)	x(x)	x(x)	x(x)	x(x)	x(x)	x(x)	x(x)	x(x)
		Median (IQR)	(x, x)	(x, x)	(x, x)	(x, x)	(x, x)					
		N	x	x	x	x	x	x	x	x	x	x
Consensus peptide pool	TNFa+ as a % of CD4+	Mean (SD)	x(x)	x(x)	x(x)	x(x)	x(x)	x(x)	x(x)	x(x)	x(x)	x(x)
		Median (IQR)	(x, x)	(x, x)	(x, x)	(x, x)	(x, x)					
		N	x	x	x	x	x	x	x	x	x	x
Consensus peptide pool	IFNG+ as a % of CD4+	Mean (SD)	x(x)	x(x)	x(x)	x(x)	x(x)	x(x)	x(x)	x(x)	x(x)	x(x)
		Median (IQR)	(x, x)	(x, x)	(x, x)	(x, x)	(x, x)					
		N	x	x	x	x	x	x	x	x	x	x

Note: Frequencies are presented as percentage format 0.00% - 99.99%

[Implementation note for above and below table, the values reported in the table are values derived from (original value - background value)]

Same format for the following tables:

Table 39: Frequencies and Function of Peripheral Blood CD4+ T cells Specific for Antigens by Time Point and Treatment Group - ICS - Per-Protocol Population**Table 40: Frequencies and Function of Peripheral Blood CD8+ T cells Specific for Antigens by Time Point and Treatment Group - ICS - Immunogenicity Population**

[note: The CD8 table should not contain IL17+ as cytokine]

Table 41: Frequencies and Function of Peripheral Blood CD8+ T cells Specific for Antigens by Time Point and Treatment Group - ICS - Per-Protocol Population

[note: The CD8 table should not contain IL17+ as cytokine]

Table 42: Frequencies and Function of Rectal Mucosal CD4+ T Cells Specific for Antigens by Time Point and Treatment Group - ICS - Immunogenicity Population

[Implementation note, the values reported in the table are values derived from (original value - background value)

The assays may be performed depending on specimen availability and interim immunogenicity analysis report]

Assay: Intracellular cytokine staining (ICS)	Phenotype	Statistic	4CMenB		Placebo	
			Day 1	Day 43	Day 1	Day 43
OMV Ng1291	IL17+ as a % of CD4+	N	x	x	x	x
		Median (IQR)	x(x, x)	x(x, x)	x(x, x)	x(x, x)
		Range	(x, x)	(x, x)	(x, x)	(x, x)
	TNFa+ as a % of CD4+	N	x	x	x	x
		Median (IQR)	x(x, x)	x(x, x)	x(x, x)	x(x, x)
		Range	(x, x)	(x, x)	(x, x)	(x, x)
	IFNG+ as a % of CD4+	N	x	x	x	x
		Median (IQR)	x(x, x)	x(x, x)	x(x, x)	x(x, x)
		Range	(x, x)	(x, x)	(x, x)	(x, x)
OMV CNG20	IL17+ as a % of CD4+	N	x	x	x	x
		Median (IQR)	x(x, x)	x(x, x)	x(x, x)	x(x, x)
		Range	(x, x)	(x, x)	(x, x)	(x, x)
	TNFa+ as a % of CD4+	N	x	x	x	x
		Median (IQR)	x(x, x)	x(x, x)	x(x, x)	x(x, x)
		Range	(x, x)	(x, x)	(x, x)	(x, x)
	IFNG+ as a % of CD4+	N	x	x	x	x
		Median (IQR)	x(x, x)	x(x, x)	x(x, x)	x(x, x)
		Range	(x, x)	(x, x)	(x, x)	(x, x)

Table 42: Frequencies and Function of Rectal Mucosal CD4+ T Cells Specific for Antigens by Time Point and Treatment Group - ICS - Immunogenicity Population (continued)

Assay: Intracellular cytokine staining (ICS)	Phenotype	Statistic	4CMenB		Placebo	
			Day 1	Day 43	Day 1	Day 43
NHBA Ng1291* peptide	IL17+ as a % of CD4+	N	x	x	x	x
		Median (IQR)	x(x, x)	x(x, x)	x(x, x)	x(x, x)
		Range	(x, x)	(x, x)	(x, x)	(x, x)
	TNFa+ as a % of CD4+	N	x	x	x	x
		Median (IQR)	x(x, x)	x(x, x)	x(x, x)	x(x, x)
		Range	(x, x)	(x, x)	(x, x)	(x, x)
	IFNG+ as a % of CD4+	N	x	x	x	x
		Median (IQR)	x(x, x)	x(x, x)	x(x, x)	x(x, x)
		Range	(x, x)	(x, x)	(x, x)	(x, x)
NHBA CNG20* peptide	IL17+ as a % of CD4+	N	x	x	x	x
		Median (IQR)	x(x, x)	x(x, x)	x(x, x)	x(x, x)
		Range	(x, x)	(x, x)	(x, x)	(x, x)
	TNFa+ as a % of CD4+	N	x	x	x	x
		Median (IQR)	x(x, x)	x(x, x)	x(x, x)	x(x, x)
		Range	(x, x)	(x, x)	(x, x)	(x, x)
	IFNG+ as a % of CD4+	N	x	x	x	x
		Median (IQR)	x(x, x)	x(x, x)	x(x, x)	x(x, x)
		Range	(x, x)	(x, x)	(x, x)	(x, x)

Note: Frequencies are presented as percentage format 0.00% - 99.99%

Same format for the following tables:

Table 43: Frequencies and Function of Rectal Mucosal CD4+ T Cells Specific for Antigens by Time Point and Treatment Group - ICS - Per-Protocol Population

Table 44: Frequencies and Function of Rectal Mucosal CD8+ T Cells Specific for Antigens by Time Point and Treatment Group - ICS - Immunogenicity Population

[note: The CD8 table should not contain IL17+ as cytokine]

Table 45: Frequencies and Function of Rectal Mucosal CD8+ T Cells Specific for Antigens by Time Point and Treatment Group - ICS - Per-Protocol Population

[note: The CD8 table should not contain IL17+ as cytokine]

Table 46: Percent Inhibition of Gonococcal Adhesion to Human Cervical Cell Line (ME180) by Mucosal Antibodies at Day 43

Population	Assay	Percent Inhibition (95% CI)	
		4CMenB	Placebo
Immunogenicity Population	N*	x	x
	BAA_1291	x(x , x)	x(x , x)
	BAA_20	x(x , x)	x(x , x)
Per-Protocol Population	N*	x	x
	BAA_1291	x(x , x)	x(x , x)
	BAA_20	x(x , x)	x(x , x)

*N =Number of participants in the certain Treatment Group for certain analysis population

Table 47: Summary of Categorical Sexual History Variables at Screening - All Enrolled Participants

Variable		Characteristic	4CMenB N=X		Placebo N=X		All Participants	
			n	%	n	%	n	%
Oral receptive	Yes/No	No	x	x	x	x	x	x
		Yes	x	x	x	x	x	x
	How often did the participant or the participant's partner use a condom or barrier for protection?	Always	x	x	x	x	x	x
		Sometimes	x	x	x	x	x	x
		Never	x	x	x	x	x	x
Oral active	Yes/No	No	x	x	x	x	x	x
		Yes	x	x	x	x	x	x
	How often did the participant or the participant's partner use a condom or barrier for protection?	Always	x	x	x	x	x	x
		Sometimes	x	x	x	x	x	x
		Never	x	x	x	x	x	x
Rectal receptive	Yes/No	No	x	x	x	x	x	x
		Yes	x	x	x	x	x	x
	How often did the participant or the participant's partner use a condom or barrier for protection?	Always	x	x	x	x	x	x
		Sometimes	x	x	x	x	x	x
		Never	x	x	x	x	x	x
Rectal insertive	Yes/No	No	x	x	x	x	x	x
		Yes	x	x	x	x	x	x
	How often did the participant or the participant's partner use a condom or barrier for protection?	Always	x	x	x	x	x	x
		Sometimes	x	x	x	x	x	x
		Never	x	x	x	x	x	x
Genital/vaginal	Yes/No	No	x	x	x	x	x	x
		Yes	x	x	x	x	x	x
	How often did the participant or the participant's partner use a condom or barrier for protection?	Always	x	x	x	x	x	x
		Sometimes	x	x	x	x	x	x
		Never	x	x	x	x	x	x

Note: N is the number of participants answered "Yes" to the question "Sexual intercourse in last 6 months?"

Table 48: Summary of Continuous Sexual History Variables at Screening - All Enrolled Participants

Variable	Statistics	4CMenB (N=x)	Placebo (N=x)	All Participants (N=x)
How many total sexual partners has the participant had in the preceding 6 months?	Mean (SD)	x(x)	x(x)	x(x)
	Median (min, max)	x(x,x)	x(x,x)	x(x,x)

Table 49: Summary of Categorical Sexual History Variables at Follow Up - All Enrolled Participants

Variable		Characteristic	Visit 01				Visit 04				Visit 04Z									
			4CMenB		Placebo		All Participants		4CMenB		Placebo		All Participants		4CMenB		Placebo		All Participants	
			n	%	n	%	n	%	n	%	n	%	n	%	n	%	n	%	n	%
Sexual intercourse ^{a,c}		Yes	X	X	X	X	X	X	X	X	X	X	X	X	X	X	X	X	X	X
New partner sexual orientation ^b		Opposite-sex	X	X	X	X	X	X	X	X	X	X	X	X	X	X	X	X	X	X
		Same-sex	X	X	X	X	X	X	X	X	X	X	X	X	X	X	X	X	X	X
		Both	X	X	X	X	X	X	X	X	X	X	X	X	X	X	X	X	X	X
Oral receptive	Yes/No	No	X	X	X	X	X	X	X	X	X	X	X	X	X	X	X	X	X	X
		Yes	X	X	X	X	X	X	X	X	X	X	X	X	X	X	X	X	X	X
	How often did the participant or the participant's partner use a condom or barrier for protection?		Always	X	X	X	X	X	X	X	X	X	X	X	X	X	X	X	X	X
Oral active	Yes/No	Always	X	X	X	X	X	X	X	X	X	X	X	X	X	X	X	X	X	X
		Sometimes	X	X	X	X	X	X	X	X	X	X	X	X	X	X	X	X	X	X
	Never		Never	X	X	X	X	X	X	X	X	X	X	X	X	X	X	X	X	X
Rectal receptive	Yes/No	No	X	X	X	X	X	X	X	X	X	X	X	X	X	X	X	X	X	X
		Yes	X	X	X	X	X	X	X	X	X	X	X	X	X	X	X	X	X	X
	Engage in receptive anal <= 1 week after the rectal biopsy procedure?		No	X	X	X	X	X	X	X	X	X	X	X	X	X	X	X	X	X
	How often did the participant or the participant's partner use a condom or barrier for protection?		Yes	X	X	X	X	X	X	X	X	X	X	X	X	X	X	X	X	X
	Always		Always	X	X	X	X	X	X	X	X	X	X	X	X	X	X	X	X	X
	Sometimes		Sometimes	X	X	X	X	X	X	X	X	X	X	X	X	X	X	X	X	X
	Never		Never	X	X	X	X	X	X	X	X	X	X	X	X	X	X	X	X	X

Table 49: Summary of Categorical Sexual History Variables at Follow Up - All Enrolled Participants (continued)

		Characteristic	Visit 01				Visit 04				Visit 04Z									
Variable			4CMenB		Placebo		All Participants		4CMenB		Placebo		All Participants		4CMenB		Placebo		All Participants	
		n	%	n	%	n	%	n	%	n	%	n	%	n	%	n	%	n	%	
Rectal insertive	Yes/No	No	x	x	x	x	x	x	x	x	x	x	x	x	x	x	x	x	x	
		Yes	x	x	x	x	x	x	x	x	x	x	x	x	x	x	x	x	x	
	How often did the participant or the participant's partner use a condom or barrier for protection?	Always	x	x	x	x	x	x	x	x	x	x	x	x	x	x	x	x	x	
		Sometimes	x	x	x	x	x	x	x	x	x	x	x	x	x	x	x	x	x	
		Never	x	x	x	x	x	x	x	x	x	x	x	x	x	x	x	x	x	
	Yes/No	No	x	x	x	x	x	x	x	x	x	x	x	x	x	x	x	x	x	
		Yes	x	x	x	x	x	x	x	x	x	x	x	x	x	x	x	x	x	
	How often did the participant or the participant's partner use a condom or barrier for protection?	Always	x	x	x	x	x	x	x	x	x	x	x	x	x	x	x	x	x	
		Sometimes	x	x	x	x	x	x	x	x	x	x	x	x	x	x	x	x	x	
		Never	x	x	x	x	x	x	x	x	x	x	x	x	x	x	x	x	x	

^a The question is: Sexual intercourse since previous visit?^b The question is: if there is new partner since previous visit, what is sexual orientation?^c if the answer to this question is "Yes" then continue.

Table 50: Summary of Continuous Sexual History Variables at Follow Up - All Enrolled Participants

Variable	Statistics	Visit 01			Visit 04			Visit 04Z		
		4CMenB (N=x)	Placebo (N=x)	All Participants (N=x)	4CMenB (N=x)	Placebo (N=x)	All Participants (N=x)	4CMenB (N=x)	Placebo (N=x)	All Participants (N=x)
How many total sexual partners has the participant had since previous visit?	Mean (SD)	x (x)	x (x)	x (x)	x (x)	x (x)	x (x)	x (x)	x (x)	x (x)
	Median (min, max)	x (x,x)	x (x,x)	x (x,x)	x (x,x)	x (x,x)	x (x,x)	x (x,x)	x (x,x)	x (x,x)
How many new sexual partners has the participant had? *	Mean (SD)	x (x)	x (x)	x (x)	x (x)	x (x)	x (x)	x (x)	x (x)	x (x)
	Median (min, max)	x (x,x)	x (x,x)	x (x,x)	x (x,x)	x (x,x)	x (x,x)	x (x,x)	x (x,x)	x (x,x)

* New partner defined as partners since the last assessment with no sexual contact in the 6 months prior to initial screening.

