3.2.3. Exploratory Outcomes

- Rectal mucosal IgG concentrations (GMT) against GC antigens before and after vaccination in each treatment group
- Serum IgG concentrations (GMT) against GC antigens before and after vaccination in each treatment group
- Vaginal mucosal IgG concentrations geometric mean titer (GMT) against GC antigens before and after vaccination in female participants in each treatment group
- Oropharyngeal mucosal IgG concentrations (GMT) against GC antigens before and after vaccination in each treatment group
- Serum IgA concentrations (GMT) against GC antigens before and after vaccination in each treatment group
- Rectal mucosal IgA concentrations (GMT) against GC antigens before and after vaccination in each treatment group
- Vaginal mucosal IgA concentrations (GMT) against GC antigens before and after vaccination in female participants in each treatment group
- Oropharyngeal mucosal IgA concentrations (GMT) against GC antigens before and after vaccination in each treatment group
- Frequencies and function of memory B cells specific for antigens from GC before and after vaccination by ELISpot in each treatment group.
- Frequencies and function of peripheral blood T cells specific for antigens from GC before and after vaccination by ELISpot in each treatment group.
- Frequencies, phenotype, and function of peripheral blood CD4+ T cells specific for antigens from GC based on cytokine profile before and after vaccination by intracellular cytokine staining in each treatment group.
- Frequencies, phenotype, and function of peripheral blood CD8+ T cells specific for antigens from GC based on cytokine profile before and after vaccination by intracellular cytokine staining in each treatment group.
- Frequencies, phenotype, and function of rectal mucosal CD4+ T cells specific for antigens from GC based on cytokine profile before and after vaccination by intracellular cytokine staining in each treatment group.
- Frequencies, phenotype, and function of rectal mucosal CD8+ T cells specific for antigens from GC based on cytokine profile before and after vaccination by intracellular cytokine staining in each treatment group.

- Serum bactericidal antibody titers against GC before and after vaccination in each treatment group.
- Percent inhibition of gonococcal adhesion to human cervical cell line (ME180) by mucosal antibodies at Day 43 in each treatment group.

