6. GENERAL STATISTICAL CONSIDERATIONS

6.1. General Principles

Unless otherwise specified, continuous variables will be summarized using the following descriptive statistics: n (non-missing sample size), mean, standard deviation, median, minimum and maximum. For some immunogenicity outcomes, the titers /frequencies will be summarized by geometric mean titer (GMT) /geometric mean titer frequencies and confidence interval (CI), fold change (rise or decline) from baseline will be calculated for the follow up immunogenicity outcomes. When calculating geometric mean, only non-zero values will be included. The frequency and percentages (based on the non-missing sample size) of observed levels will be reported for all categorical measures. Exact confidence intervals for binomial proportions will be computed for safety variables. In general, all data will be listed, sorted by Treatment group, and participant, and when appropriate by visit number within participant. All summary tables will be structured with a column for each Treatment in the order presented and will be annotated with the total population size relevant to that table/treatment, including any missing observations.

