8.3. Exploratory Outcome Analyses

For the exploratory outcomes, summaries of IgG antibody concentrations (GMT) at each time point and GMFR in each treatment group are shown in [Table 18](#), [Table 19](#), [Table 20](#), and [Table 21](#). Summaries of the ratio of serum to mucosal IgG GMT results will be presented in [Table 22](#) and [Table 23](#). Summaries of pairwise ratios of mucosal IgG concentrations among anatomical sites will be generated at each time point and presented in [Table 24](#) and [Table 25](#). Summaries of IgA antibody concentrations and serum bactericidal antibody (GMT) at each time point and GMFR for other exploratory outcomes are shown starting in [Table 26](#) and concluding with [Table 33](#). Serum Bactericidal Antibody GMT and GMFR will be presented in [Table 34](#).

Summaries of the frequency of antigen-specific immune cells will include the mean if data are reported as percentage, or geometric mean if data are reported as cell count per million cells. The corresponding 95% confidence interval as well as the median, minimum, and maximum values will be presented. Fold rise from baseline will be summarized by arithmetic, geometric mean^[2] or median. The summary of frequencies will be presented starting in [Table 35](#) and concluding with [Table 45](#). Figures depicting the GMT (IgG, IgA) or frequency (MBC, T cells) for each assay over time will be presented beginning with [Figure 10](#) and continuing through [Figure 39](#) (GMTs), and [Figure 74](#) to [Figure 87](#) (frequencies). Reverse cumulative distribution (RCD) plots will be presented with separate panels for each visit, and separate curves within each panel for

each study arm and overall. Antibody titers are shown beginning with **Figure 40** and continuing through **Figure 73**. Percent inhibition of gonococcal adhesion to human cervical cell line (ME180) by mucosal antibodies at day 43 in each treatment group will be show in **Table 46**. The results for each participant at each visit are listed in **Listing 11** through **Listing 22**.

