[note: The assays may be performed depending on specimen availability and interim immunogenicity analysis report]

Table 32: Oropharyngeal Mucosal IgA against OMV antigens: GMT and GMFR Results Time Point and Treatment Group

Table 33: Oropharyngeal Mucosal IgA against NHBA antigens: GMT and GMFR Results Time Point and Treatment Group

[note: The assays may be performed depending on specimen availability and interim immunogenicity analysis report]

Table 34: Serum Bactericidal antibody GMT and GMFR Results against N. Gonorrhoeae by Time Point and Treatment Group

Table 35: Frequencies of Memory B Cells Specific for OMV and NHBA Antigens by Time Point and Treatment Group

Population	Assay: IgG MBC ELISpot	Statistic	4CMenB				Placebo			
			Day 1	Day 29	Day 43	Day 181	Day 1	Day 29	Day 43	Day 181
Immunogenicity Population	OMV NZ98	N	x	x	x	x	x	x	x	x
		Mean (SD)	x(x)							
		Median (Range)	x(x, x)							
	OMV Ng1291	N	x	x	x	x	x	x	x	x
		Mean (SD)	x(x)							
		Median (Range)	x(x, x)							
	OMV CNG20	N	x	x	x	x	x	x	x	x
		Mean (SD)	x(x)							
		Median (Range)	x(x, x)							
	NHBA NZ98	N	x	x	x	x	x	x	x	x
		Mean (SD)	x(x)							
		Median (Range)	x(x, x)							
	NHBA Ng1291	N	x	x	x	x	x	x	x	x
		Mean (SD)	x(x)							
		Median (Range)	x(x, x)							
	NHBA CNG20	N	x	x	x	x	x	x	x	x
		Mean (SD)	x(x)							
		Median (Range)	x(x, x)							

Table 35: Frequencies of Memory B Cells Specific for OMV and NHBA antigens by Time Point and Treatment Group (continued)

Population	Assay: IgG MBC ELISpot	Statistic	4CMenB				Placebo			
			Day 1	Day 29	Day 43	Day 181	Day 1	Day 29	Day 43	Day 181
Per-protocol Population	OMV NZ98	N	x	x	x	x	x	x	x	x
		Mean (SD)	x(x)							
		Median (Range)	x(x, x)							
	OMV Ng1291	N	x	x	x	x	x	x	x	x
		Mean (SD)	x(x)							
		Median (Range)	x(x, x)							
	OMV CNG20	N	x	x	x	x	x	x	x	x
		Mean (SD)	x(x)							
		Median (Range)	x(x, x)							
Per-protocol Population	NHBA NZ98	N	x	x	x	x	x	x	x	x
		Mean (SD)	x(x)							
		Median (Range)	x(x, x)							
	NHBA Ng1291	N	x	x	x	x	x	x	x	x
		Mean (SD)	x(x)							
		Median (Range)	x(x, x)							
	NHBA CNG20	N	x	x	x	x	x	x	x	x
		Mean (SD)	x(x)							
		Median (Range)	x(x, x)							

Notes: N is the number of participants in each group at given timepoint.
Frequencies are % total IgG-secreting memory B cells (format: 0.00-XXX)

Table 36: Frequencies of Peripheral Blood T Cells Specific for OMV Antigens by Time Point and Treatment Group

Population	Assay: IFNg ELISpot	Statistic	4CMenB							Placebo						

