Figure 64: Reverse Cumulative Distribution of Vaginal Mucosal IgA Antibody Against OMV by Study Day and Treatment Group - Immunogenicity Population

Figure 65: Reverse Cumulative Distribution of Vaginal Mucosal IgA Antibody Against OMV by Study Day and Treatment Group - Per-Protocol Population

Figure 66: Reverse Cumulative Distribution of Vaginal Mucosal IgA Antibody Against NHBA by Study Day and Treatment Group - Immunogenicity Population

Figure 67: Reverse Cumulative Distribution of Vaginal Mucosal IgA Antibody Against NHBA by Study Day and Treatment Group - Per-Protocol Population

Figure 68: Reverse Cumulative Distribution of Oropharyngeal Mucosal IgA Antibody Against OMV by Study Day and Treatment Group - Immunogenicity Population

Figure 69: Reverse Cumulative Distribution of Oropharyngeal Mucosal IgA Antibody Against OMV by Study Day and Treatment Group - Per-Protocol Population

Figure 70: Reverse Cumulative Distribution of Oropharyngeal Mucosal IgA Antibody Against NHBA by Study Day and Treatment Group - Immunogenicity Population

[figure not shown]
Figure 71: Reverse Cumulative Distribution of Oropharyngeal Mucosal IgA Antibody Against NHBA by Study Day and Treatment Group - Per-Protocol Population

Figure 72: Reverse Cumulative Distribution of Serum Bactericidal Antibody Against GC Study Day and Treatment Group - Immunogenicity Population

Figure 73: Reverse Cumulative Distribution of Serum Bactericidal Antibody Against GC by Study Day and Treatment Group - Per-Protocol Population

Figure 74: Frequencies and Function of Memory B Cells Specific for OMV and NHBA Antigens by Time Point and Treatment Group - Immunogenicity Population

[Implementation Note: A generic sample figure is shown below. Planned study day is plotted along the x-axis, with visit labels as tick labels. Titer/frequency is plotted on the y-axis (Scale will be determined for NZ98, Ng1291 and CNG20 from OMV or NHBA separately based on the distribution of the data received). Frequency will be plotted at each visit with upper and lower error bars for the 95% CI for each study arm with different marker shapes/colors for each study arm.]

Figures with similar format:

Figure 75: Frequencies and Function of Memory B Cells Specific for OMV and NHBA Antigens by Time Point and Treatment Group - Per-Protocol Population

Figure 76: Frequencies and Function of Peripheral Blood T Cells Specific for OMV Antigens by Time Point and Treatment Group - Immunogenicity Population

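### SAP 8.3 plans a 95% CI and a fold rise from baseline for the B-cell and T-cell frequencies, but the shells for Tables 35–45 omit the change, mostly omit the CI, and the planned ratio does not suit these assays

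*SAP*

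**What the plan says.** The exploratory outcomes in SAP 3.2.3 are worded as cell frequencies before and after vaccination by arm, for example "Frequencies and function of memory B cells specific for antigens from GC before and after vaccination by ELISpot in each treatment group".

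SAP 8.3 sets out how they are summarised. The mean is used for data reported as percentages and the geometric mean for counts per million. On precision and spread it adds: "The corresponding 95% confidence interval as well as the median, minimum, and maximum values will be presented". On change it says "Fold rise from baseline will be summarized by arithmetic, geometric mean" or the median. On location, "The summary of frequencies will be presented starting in" Table 35 and ends at Table 45. SAP 6.1 says more generally that "fold change (rise or decline) from baseline will be calculated for the follow up immunogenicity outcomes", and that only non-zero values enter a geometric mean.

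The shells in SAP Appendix 1 run from Table 35 ("Frequencies of Memory B Cells Specific for OMV and NHBA Antigens by Time Point and Treatment Group"), through Table 38 ("Frequencies of Peripheral Blood CD4+ T Cells Specific for OMV and NHBA Antigens by Time Point and Treatment Group"), to Table 45, rectal CD8+ T cells. For Figures 74–87, the Appendix 2 note says: "Frequency will be plotted at each visit with upper and lower error bars for the 95% CI for each study arm".

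**The concern.** The shells are what a programmer builds from. Built as drawn, Tables 35–45 would show each visit separately, with no estimate of how much a participant's cells changed and, in most tables, no interval. N is counted visit by visit, so two columns may describe partly different people. A reader wanting the response to vaccination would have to compare visit summaries by eye, and its precision cannot be recovered from them because the correlation between visits is not shown. This touches the systemic B-cell, systemic T-cell and rectal T-cell objectives. It bites most where numbers are smallest: about 10 placebo participants for the blood assays and 4 for rectal T cells (Protocol 3.1).

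Second, the measure that 8.3 names for change is not settled by assay and may not be computable. SAP 3.3.2 defines the antibody fold rise per participant, with a CI. The cell assays have no such definition.

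**Working it through.** **Step 1. Text against shells.** The plan states no figure to reproduce here, so the check is a row-by-row comparison of SAP 8.3 with Appendix 1.

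| Tables | Assay and unit | Rows at each visit | 95% CI | Change from baseline |
|---|---|---|---|---|
| 35 | Memory B cells, % | N, mean (SD), median (range) | No | No |
| 36, 37 | T-cell ELISpot, spots per million | N, geometric mean, CI | Yes | No |
| 38, with 39–41 in the same format | Blood ICS, % | N, mean (SD), median (IQR) | No | No |
| 42, with 43–45 in the same format | Rectal ICS, % | N, median (IQR), range | No | No |

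Tables: 1 + 2 + 4 + 4 = 11. With a CI: 2. Without: 1 + 4 + 4 = 9. With a change row: 0.

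Tables 36 and 37 also lack the median, minimum and maximum that 8.3 lists. Tables 42–45 lack the mean, although their data are percentages.

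**Step 2. Can the missing CI be derived?** A t-based CI for a mean has half-width t(0.975, n−1)/√n in SD units.

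- Tables 35 and 38–41 give N, mean and SD, so a reader could compute it: 2.023/√40 = 0.32 SD at n=40, and 2.262/√10 = 0.72 SD at n=10.
- Tables 42–45 give neither mean nor SD, so it cannot be computed. For scale it would be 2.131/√16 = 0.53 SD at n=16 and 3.182/√4 = 1.59 SD at n=4.

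**Step 3. Is fold rise workable?**

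- ICS values are reported after background is subtracted (notes to Tables 38 and 42). They can be zero or negative, and a ratio of such values has no useful meaning.
- Memory B-cell and ELISpot formats start at 0. A zero baseline makes the ratio undefined. A zero at follow-up gives a ratio of zero, which the 6.1 rule then removes from the geometric mean. The participants lost would be those with the lowest values.

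**Step 4. What does pairing gain?** Assume equal variance s² at both visits, n complete pairs and correlation r. The documents give no r; 0.5 to 0.8 is assumed.

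- Paired change: variance 2s²(1−r)/n. Two independent visit means: 2s²/n. SE ratio = √(1−r): 0.71 at r=0.5, 0.55 at r=0.7, 0.45 at r=0.8.
- The CI-width ratio must also allow for degrees of freedom, n−1 against 2n−2: [t(n−1)/t(2n−2)] × √(1−r).
- n=10: 2.262/2.101 = 1.077, giving 0.76, 0.59 and 0.48. The paired CI is 24–52% narrower across the range.
- n=4: 3.182/2.447 = 1.300, giving 0.92, 0.71 and 0.58. It is 8–42% narrower.
- Break-even at n=4: 1−r = (2.447/3.182)² = 0.59, so r = 0.41. Below that the paired CI is wider; at r=0.3 the ratio is 1.300 × 0.837 = 1.09.

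For spots per million the same algebra applies on the log scale.

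**The case against.** A reader of the shells might infer that the before-and-after outcomes are never estimated. The documents do not support that. SAP 8.3 plans a fold rise and a 95% CI for these frequencies, 6.1 plans fold change for follow-up immunogenicity outcomes, Figures 74–87 carry per-visit CIs by arm, and the SAP preface presents its tables as samples. The outcome wording also names no change-from-baseline estimand, so per-visit summaries by arm do report the outcome as written. Nothing in the plan proposes to compare visits as independent groups, and Listings 15–21 show values by participant and time point, so pairing is not lost from the report. All of this stands.

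A reader might also take √(1−r) as the CI saving and conclude 29–55% narrower intervals throughout. That is an SE ratio, and the gain at n=4 is much smaller. Nor is it true that every ELISA table carries a fold rise: the ratio Tables 22–25 do not.

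The stakes are modest. The outcomes are exploratory, the trial tests no hypotheses, the results go to a CSR addendum, and the rectal assays may be run only if specimens and the interim results allow.

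What the objection does not answer is that the text and shells disagree, that no figure or listing shows a change, and that 8.3 neither assigns a measure to each assay nor gives it a CI. Following 8.3 literally would still produce ratios that are meaningless or undefined for some participants.

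**Conclusion.** The point holds as a mismatch between SAP 8.3 and its shells, together with a change measure that is unsettled and ill-suited to the data. It is not a missing analysis. The count of 0 of 11 tables with a change row and 9 of 11 without a CI rests on the shells as printed. The precision figures rest on an assumed r of 0.5 to 0.8, equal variances and complete pairs: an SE 0.71 to 0.45 times as large, and a CI about 24–52% narrower at n=10 and 8–42% narrower at n=4, where any gain needs r above about 0.41. Because the outcomes are exploratory and descriptive, this is a worthwhile improvement that does not threaten the trial's main conclusions.

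**What to change.** In Tables 35–45, for each antigen, post-baseline visit and arm, add the number of participants with both values and the within-participant change from baseline with its 95% CI:

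- **Percentage assays (memory B cells, blood and rectal ICS):** the paired difference in percentage points.
- **Spots per million (Tables 36 and 37):** the geometric mean of individual follow-up-to-baseline ratios, with a prespecified floor value for zeros so that no participant is dropped.

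Rewrite the fold-rise sentence in 8.3 to name these measures by assay, and state in 6.1 that the floor replaces the exclusion of zeros here. Add the per-visit 95% CI that 8.3 promises to Tables 35 and 38–45; in Tables 42–45 that means adding the mean as well.

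The cost is a SAP text and shell edit, routine programming once the floor is chosen, and longer tables. It uses data already planned for collection and leaves trial conduct unchanged.
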